4. STUDY POPULATION

Three hundred men and women over the age of 75 years will be recruited and screened for the presence of systolic hypertension and WMH volume of $\geq 0.5\%$ on MRI. It is expected that 2 of 3 patients in this age group will have WMH. Of the screened patients, 200 will be randomized in a 1:1 ratio to either the intensive or standard treatment arms. Every attempt will be made to have a substantial representation of minorities who have hypertension. It is estimated that 15% of the study population will be African-American and 10% will have Hispanic/Latino ethnicity. The inclusion and exclusion criteria for study entry are as follows:

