8.3 Sample Size and Randomization

We conservatively estimate that at least 140 of the original 200 participants will complete assessments at 35 months. We analyzed a subset of participants in our earlier observational study in order to mimic the results of the two treatment groups we expect to see in the intervention study. For a standard care arm, we selected participants in the observational study who had 24 hour systolic BP between 140 and 150 mmHg, inclusive, at follow-up, and for the intensive treatment arm, we selected participants with 24 hour Systolic BP between 120 and 130 mmHg, inclusive, at follow-up. A regression of gait velocity over 8 feet on our covariates age, sex, and 24 hour systolic BP at baseline showed an r^2 of 0.1267. If we see similar results in the intervention study, 140 participants (70 in each group) will give us 85% power to observe an increase in r^2 of 0.0533 to 0.1800. In our prior observational study, we saw an increase in r^2 of 0.1082 to 0.2349, with a difference in gait speed between the two simulated treatment groups of 0.15m./sec. While the 0.15m/sec gait speed difference between the low and high BP groups appears small, it represents only 2 years of observation. Mobility impairment linked to WMH is a long-term decremental process that limits gait velocity over 10 or more years. Thus a “small” 2-year differential is both believable and meaningful. We are therefore confident that the proposed study has ample power to find smaller yet clinically significant effects for our primary outcome. A regression of total WMH on covariates age, sex, and 24 hour systolic BP at baseline showed an r^2 of 0.1162. Similar results in the intervention study imply 85% power to observe an increase in r^2 of 0.0540 for the effect of the treatment arm, to 0.1702. We actually observed an increase of 0.0861, to 0.2023, in the prior observational study, corresponding to a difference between the two simulated treatment groups of 0.93% total WMH.

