Here, x_i is the treatment group indicator for participant i (one for intervention, zero for comparison); Y_{i1} is the WMH % for participant i at time 1 (baseline); Y_{i2} is the WMH % for participant i at time 2 (36 month follow-up); β_0 is interpreted as the average WMH % at baseline in the reference group; β_C is interpreted as the difference in the average WMH % at baseline between the intervention group and the reference group and will be zero if the two groups are exactly comparable in their baseline values; β_L is interpreted as the average change in WMH % between 36 month follow up and baseline in the reference group; β_T is interpreted as the difference average change in WMH % between 36 month follow up and baseline between the intervention group and the reference group and thus the parameter of primary interest; γ_i is a random intercept for participant i that addresses the correlation in WMH % across the two time points; and ε_{i1} and ε_{i2} are the residual error terms at baseline and follow-up, respectively. All analyses will be repeated as stratified analyses (b - e below).

- b. Stratified according to < or > median age
- c. Stratified according to gender
- d. Stratified according to median years of education
- e. Stratified according to a clinical diagnosis of minor or major depression
- f. Stratified according to presence or absence of statin therapy for hyperlipidemia
- g. Stratified according to presence or absence of anti-platelet therapies (aspirin, clopidigrel)
- h. Sensitivity analysis at 36 months by ambulatory systolic BP : rationale – for study patients who either never met the achieved BP for their group assignment or who shifted mid-trial to an ambulatory BP

value out of alignment with their assigned treatment group (e.g. a standard group patient whose 24 hour systolic BP was < 135 mmHg would be excluded from the sensitivity analysis; an intensive group patient whose 24 hour systolic BP was > 135 mmHg would be excluded from the sensitivity analysis).

2. Change in mobility, cognition and depression from baseline to 3 years
 - a. According to treatment group (primary analysis)

$$Y_{i1} = \beta_0 + \beta_C x_i + \gamma_i + \varepsilon_{i1}$$

$$Y_{i2} = \beta_0 + \beta_C x_i + \beta_L + \beta_T x_i + \gamma_i + \varepsilon_{i2}$$

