Here, x_i is the treatment group indicator for participant i as in (1); Y_{i1} is the mobility score for participant i at time 1 (baseline); Y_{i2} is the mobility score for participant i at time 2 (36 month follow-up); β_0 is interpreted as the average mobility score at baseline in the reference group; β_C is interpreted as the difference in the average mobility score at baseline between the intervention group and the reference group and will be zero if the two groups are exactly comparable in their baseline values; β_L is interpreted as the average change in mobility between 36 month follow up and baseline in the reference group; β_T is interpreted as the difference average change in mobility between 36 month follow up and baseline between the intervention group and the reference group and thus the parameter of primary interest; γ_i is a random intercept for participant i that addresses the correlation in mobility across the two time points; and ε_{i1} and ε_{i2} are the residual error terms at baseline and follow-up, respectively.

This analysis will be repeated for each mobility parameter (gait speed, four stair ascent and descent time, supine to sit time), cognition scores (Trailmaking A and B, Stroop Color & Word score, and simple reaction time), and the Geriatric Depression Scale. The timed measures – Trailmaking A and B, and simple reaction time – will be inverse-transformed so that they have a speed interpretation; this will also reduce the influence of outliers. Similarly, all analyses will be repeated as stratified analyses (b - e below).

- b. Stratified according to < or > median age
- c. Stratified according to gender
- d. Stratified according to median years of education
- e. Stratified according to a clinical diagnosis of minor or major depression (for mobility and cognition)

3. Change in urinary severity index and depression category (based on the Geriatric Depression Scale) from baseline to 3 years. These analyses will be similar to the analyses for white matter hyperintensities in (1) and for mobility and cognition in (2), but using ordinal logistic regression.
 - a. According to treatment group (primary analysis)

$$\log(Y_{i1} > k / Y_{i1} \leq k) = \beta_{0k} + \beta_C x_i + \gamma_i$$

$$\log(Y_{i2} > k / Y_{i2} \leq k) = \beta_{0k} + \beta_C x_i + \beta_L + \beta_T x_i + \gamma_i$$

$$k = 1, \dots, m - 1$$

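### SAP items 1–5 repeat the treatment model stratum by stratum without estimating how the effect differs between strata; item 6 fills this gap only in part, for age and sex

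*SAP*

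**What the plan says.** SAP item 1 fits a treatment-by-time model for WMH with beta_T, the between-arm difference in change to month 36, as the parameter of interest. It then states: "All analyses will be repeated as stratified analyses (b - e below"). The list under item 1 in fact has six stratifying factors (b to g): age, gender, education, depression, statin therapy and antiplatelet therapy. Item 2 repeats the instruction for mobility, cognition and depression scores ("all analyses will be repeated as stratified analyses (b - e below")), and items 3 to 5 list the same first four factors for urinary severity and depression category, DTI, and the sleep and SF-36 scales. The age split reads "Stratified according to < or > median age".

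None of items 1–5 contains a treatment-by-time-by-subgroup term, a heterogeneity test, a multiplicity rule or a rule for reading the strata. Item 3 calls beta_T an interaction, but that is treatment by time.

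Item 6 is the exception. Its model has a term theta_INT multiplying treatment by the change in WMH, and a secondary analysis puts age, sex or month-36 systolic BP in place of that change, with bootstrap standard errors and intervals. The SAP introduces its additions as secondary analyses specified before database lock.

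**The concern.** A stratified refit gives one treatment estimate per stratum. It does not say whether those estimates differ by more than chance. When each stratum holds only part of a modest sample, one will often reach significance and the other will not, even where treatment works equally in both. Unless the difference is estimated with an interval, readers have only the two stratum results to compare, and a pattern of one significant and one not is easily taken as effect modification. With several factors and many outcomes, a number of such patterns will arise by chance.

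**Working it through.** **1. Reproduce the planned power.** Inputs are from Protocol section 8.3, Sample Size and Randomization: "A regression of gait velocity over 8 feet on our covariates age, sex, and 24 hour systolic BP at baseline showed an r^2 of 0.1267", and "140 participants (70 in each group) will give us 85% power to observe an increase in r^2 of 0.0533 to 0.1800". Neither document states alpha, so 0.05 two-sided is assumed.

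- f² = 0.0533 / (1 − 0.1800) = 0.065; noncentrality = 140 × 0.065 = 9.1; F test on 1 and 135 df.
- Power = 84.97%, which matches the stated 85%. Alpha 0.10 would give 91.3% and alpha 0.025 would give 77.3%, so 0.05 is the value that fits.
- The WMH statement ("85% power to observe an increase in r^2 of 0.0540 for the effect of the treatment arm, to 0.1702") gives 85.01% by the same route.

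**2. Identical true effect in both strata.** Stratum sizes are not given, so a range is shown. The same F test is applied within each stratum. The chance that exactly one is significant is a(1 − b) + b(1 − a), where a and b are the stratum powers.

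| Split of 140 | Power in each stratum | Exactly one significant |
|---|---|---|
| 70 / 70 | 55.6%, 55.6% | 2 × 0.556 × 0.444 = 49% |
| 42 / 98 (30/70) | 36.3%, 70.5% | 56% |
| 28 / 112 (20/80) | 25.3%, 76.2% | 63% |

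With no effect in either stratum the figure is 2 × 0.05 × 0.95 = 9.5%. In 200,000 simulated trials with equal strata and an identical effect, an interaction test was significant in 4.98% of all trials and in about 10% of those with discordant strata.

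**3. Number of comparisons.** The count takes two strata per factor, all six listed WMH factors, FA and MD as the two DTI outcomes, and SF-36 as one score.

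- Item 1: 1 outcome × 6 factors = 6
- Item 2: 8 mobility and cognition outcomes × 4, plus the Geriatric Depression Scale × 3 (not stratified by depression) = 35
- Item 3: 2 × 4 = 8
- Item 4: 2 × 4 = 8
- Item 5: 3 × 4 = 12
- Total: 69 outcome-by-factor pairs, or 138 stratum tests

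Under a global null, 138 × 0.05 = 6.9 stratum tests would be significant and 69 × 0.095 = 6.6 pairs would be discordant. Correlation between outcomes does not change these expected counts. If the sentence in item 1 is taken literally (b to e), the totals are 67 pairs, 134 tests and 134 × 0.05 = 6.7.

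**4. What item 6 covers.** In the item 6 model theta_INT appears only in the month-36 equation. With age or sex substituted, it is algebraically the dependence of the treatment effect on change upon age or sex. Item 6 builds on the 9 outcomes of item 2 and the 2 of item 3, so it reaches 11 × 2 = 22 of the 69 pairs. The remaining 47 have no interaction estimate.

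**5. Power of the interaction test.** The standardised planned effect is d = 2√0.065 = 0.51. With equal strata the standard error of the interaction is √(4/70 + 4/70) = 0.338. For an interaction equal to d, power is Φ(0.51/0.338 − 1.96) = 33%. For one twice as large it is 85%. The interaction detectable with 80% power is (1.96 + 0.84) × 0.338 = 0.95.

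**The case against.** A reader might infer that the SAP contains no treatment-by-subgroup term and no interval for one. Item 6 contradicts that for age and sex on the item 2 and 3 outcomes, about a third of the pairs. What limits item 6 is its presentation. The named outputs are a controlled direct effect, a reference interaction, a mediated interaction and a pure indirect effect, rather than the contrast between strata. Nothing links them to the strata in items 1–5. The protocol's remark on interactions with treatment group, under Hypothesis 4, concerns imaging predictors and does not help.

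A reader might also infer that every outcome is stratified. The adverse events in item 7 are not, and the statin and antiplatelet strata apply to WMH only.

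The strongest objection is that stratum estimates are a legitimate descriptive output. The SAP calls the additions secondary, and it nowhere says that a subgroup claim will be made from a within-stratum p-value. That stands: over-reading is a risk, and the plan does not commit to it. But the secondary label does not supply the missing quantity, the difference in effect with its uncertainty.

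Finally, interaction tests do not solve multiplicity. At 0.05, 69 × 0.05 = about 3.5 of them would be significant by chance. This also stands, and is a reason to label the results exploratory.

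**Conclusion.** The point holds for the stratified analyses in items 1–5 and does not affect the primary efficacy analysis. There is no estimate or test of a between-stratum difference for the education, depression, statin or antiplatelet strata, nor for any stratum of WMH, DTI, sleep or SF-36. For age and sex on the other outcomes there is a partial substitute under a mediation label.

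The 49% to 63% range is an illustration. It rests on an assumed two-sided alpha of 0.05, on 140 completers, on the assumed stratum sizes, and on carrying the power of the protocol's covariate-adjusted month-36 regression over to the SAP's unadjusted change model. The protocol states that power for gait velocity and WMH only. The count of 69 depends on the readings listed with it.

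The literal age split gives no stratum to anyone exactly at the median. That is a minor wording point. The documents do not show that such participants would be dropped.

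**What to change.** For each subgroup factor in items 1–5, fit one model on all participants. With s as the subgroup indicator, add s and s × treatment at both times, and s × time and s × treatment × time at month 36. For item 3 the same terms go on the log-odds scale. The last coefficient is the difference between strata in the treatment effect on change. Report it with a 95% CI and p-value, and show the stratum estimates descriptively, for example in a forest plot.

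State in the SAP that no subgroup claim will rest on a within-stratum p-value and that all subgroup results are exploratory. Write the age split as ≤ median versus > median.

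The cost is SAP wording and four extra terms per model. The real downside is low power, about 33% for an interaction as large as the planned effect, so few subgroup differences could be established and a non-significant interaction should not be read as evidence of a uniform effect.

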7. STATISTICAL CONSIDERATIONS

7.1 General Design Issues

General considerations: Predictor, covariate, and dependent variables will be examined for outliers and data beyond the range of human performance. We will analyze variables on the original measurement scale, or on a scale that allows meaningful interpretation e.g., when an inverse transformation on a time measure results in a speed interpretation. The primary analyses (hypotheses 1, 2 and 3) will be intention-to-treat.

Hypothesis models, analysis plan, and power estimates for primary outcomes were developed with PASS 2008³⁵ and SAS PROC POWER³⁶ were used for estimation of power.

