8.2 Hypotheses and Statistical Analyses

The Figure shows graphically how our hypotheses relate to one another. Hypothesis 1 tests the combined effects of paths A, B, C, D & E i.e., the total effect of BP on mobility. Hypothesis 2 tests path A, Hypothesis 3 tests path D, Hypothesis 4 tests path B+E; together Hypotheses 2, 3 and 4 together test the effect of BP on mobility mediated through BP's effects on WMH and WM microstructure. Hypothesis 5 tests the relative importance of paths A and B to that of path C, i.e., the degree to which the effect of BP on mobility is explained by WMH. Hypothesis 6 tests the relative importance of paths D and E to that of path C, i.e., the degree to which the effect of BP on mobility is explained by changes in WM microstructure.

Hypothesis path diagram

Hypothesis 1: Intensively treating 24-h systolic BP to a goal of <130 mmHg versus standard BP control of <145 mmHg will lead to faster walking speeds at T₃₆. (Paths A&B+C+D&E)

Hypothesis 2: Intensively treating 24-h systolic BP to a goal of <130 mmHg versus standard BP

control <145 mmHg will lead to smaller total WMH volume. (Path A)

Hypothesis 3: Intensively treating 24-h systolic BP to a goal of <130 mmHg versus standard BP

control <145 mmHg will stabilize brain WM microstructural integrity (FA and MD) at T₃₆. (Path

D) We will perform 3 sets of analyses for hypotheses 1, 2 & 3:

- a. Multiple linear regression will be performed with treatment group (intensive vs. standard) as the predictor of interest. Gait velocity at T₃₆ is the primary outcome for hypothesis 1, WMH at T₃₆ is the primary outcome for hypothesis 2, and DTI indices (FA and MD) are the primary outcomes for hypothesis 3. The analysis will be intention-to-treat. Age, sex, and 24 hour SBP at T₀ (baseline) will be included as covariates, along with other demographic factors for which the treatment groups are not comparable. **The analysis for hypothesis 1 is the proposal's primary efficacy analysis and thus the proposal is powered to address this analysis (see Sample size estimation).**

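### The SAP treatment models omit age, sex and baseline 24-h systolic BP without giving a reason, so the protocol's 85% power, which rests on those covariates, does not describe them

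*SAP*

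**What the plan says.** **Protocol.** Section 8.2 (Hypotheses and Statistical Analyses), analysis a, is a regression on treatment arm of the month-36 value, which for hypothesis 1 is gait velocity. It states that "Age, sex, and 24 hour SBP at T₀ (baseline) will be included as covariates". The protocol names the hypothesis 1 version as the primary efficacy analysis, the one the trial is powered for. The longitudinal model in analysis c also carries cross-sectional and longitudinal covariates.

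Section 8.3 (Sample Size and Randomization) takes from the earlier cohort a regression of gait velocity "on our covariates age, sex, and 24 hour systolic BP at baseline showed an r^2 of 0.1267". It concludes that "140 participants (70 in each group) will give us 85% power to observe an increase in r^2 of 0.0533 to 0.1800". The parallel statement for white-matter hyperintensity (WMH) is "85% power to observe an increase in r^2 of 0.0540 for the effect of the treatment arm, to 0.1702".

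**SAP (24 September 2018).** Items 1a, 2a, 4a and 5a use a two-visit random-intercept model with arm, visit and arm by visit. In item 2a, which includes gait speed, "x_i is the treatment group indicator for participant i as in (1"; no other participant-level predictor enters. Item 3a is the ordinal logistic counterpart. None contains age, sex or baseline 24-h systolic BP. Age and sex appear elsewhere as strata (b and c), as candidate mediators in item 6 and as predictors of adverse events in item 7.

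The SAP's introduction describes its additions as secondary analyses, yet items 1a to 4a are each tagged as the primary analysis. Item 5a is not.

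**The concern.** Two things changed between protocol and SAP with no explanation. The prespecified covariates disappeared, and the estimand moved from an adjusted month-36 value to an unadjusted difference in change. The power statement was written for the first analysis only, and the SAP gives none for the second.

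Three things are at stake. A reader may attach the 85% to a model it was never computed for. Some precision may be given up although the covariates are measured in everyone before randomisation. And with two candidate gait-speed analyses, one adjusted and one not, it is unclear which result is primary unless that is settled before database lock.

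**Working it through.** **Inputs.** N = 140 completers, 70 per arm; r² increase 0.0533; full r² 0.1800; covariate r² 0.1267 from three covariates (protocol 8.3). For WMH: increase 0.0540, full r² 0.1702. Protocol section 4 says "200 will be randomized in a 1:1 ratio", and section 8.3 expects that "at least 140 of the original 200 participants will complete assessments". Alpha is not stated; two-sided 0.05 is assumed because it reproduces the stated power (one-sided 0.05 gives 91.3%). The baseline-to-36-month correlation ρ of gait velocity is not given; I take 0.3 to 0.8.

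**1. Reproduce the 85%.** Noncentral F test, 1 numerator df, four predictors, denominator df = 140 − 4 − 1 = 135.
λ = N × increase / (1 − full r²) = 140 × 0.0533 / 0.8200 = 9.10, power 85.0%.
WMH: 140 × 0.0540 / 0.8298 = 9.11, power 85.0%. Both reproduce.

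**2. The same month-36 regression without covariates.** Denominator df = 138.
λ = 140 × 0.0533 / (1 − 0.0533) = 7.88, power 79.6%.
WMH: 140 × 0.0540 / 0.9460 = 7.99, power 80.2%.
This loss applies at the minimum detectable increase. At the increase seen in the cohort (0.1082, to 0.2349), power is 99.3% adjusted and 98.4% unadjusted.

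**3. The SAP change model.** With two visits and complete pairs, β_T is the difference between arms in mean change. Set the total month-36 variance to 1. Under 1:1 randomisation an r² share of 0.0533 corresponds to δ = 2√0.0533 = 0.462, with within-arm variance 0.9467. Assuming equal variance at both visits, the variance of change is 0.9467 × 2(1 − ρ), so
λ = 140 × 0.0533 / [0.9467 × 2(1 − ρ)] = 7.88 / [2(1 − ρ)], df 138.

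| ρ | λ | power |
|---|---|---|
| 0.3 | 5.63 | 65.4% |
| 0.4 | 6.57 | 72.1% |
| 0.5 | 7.88 | 79.6% |
| 0.57 | 9.1 | about 85% |
| 0.6 | 9.85 | 87.6% |
| 0.7 | 13.14 | 94.9% |
| 0.8 | 19.71 | 99.3% |

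At ρ = 0.5 the divisor 2(1 − ρ) equals 1, which is why that row matches step 2.

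**4. What adjustment could add to the change model.** A covariate main effect shifts both visits equally and cancels from the change in complete pairs; only its interaction with visit can help. If the three covariates explain a share R of the within-arm variance of change (not given; 2% to 10% assumed), λ becomes λ / (1 − R) with df 135.
ρ = 0.6: 9.85 / 0.98 = 10.05 and 9.85 / 0.90 = 10.95, so 87.6% rises to between 88.3% and 90.7%.
ρ = 0.3, R = 10%: 5.63 / 0.90 = 6.26, so 65.4% rises to 70.0%.

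**The case against.** The strongest reply is that nothing powered has changed. The SAP presents itself as adding secondary analyses, never withdraws protocol analysis a, and may use its primary tag only to set each treatment comparison apart from the stratified repeats below it. An unadjusted randomised comparison is also valid. Both points stand. But the SAP does not say that the protocol regression still governs, and its tag on a model that includes gait speed leaves the matter open.

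A reader might infer from step 2 that the SAP models have about 80% power. The documents do not support this. The 79.6% belongs to a month-36 regression on arm alone, which neither document proposes. The SAP model uses the baseline outcome, and its power may fall below or well above 85%. Nor does r² = 0.1267 measure what is lost, since it describes gait level and not change.

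A reader might also infer that leaving out age biases the arm difference, because about 30% are expected to drop out and the protocol links attrition to age-related disease. That goes too far. If age-related dropout is equal in the two arms and age acts additively on change, completers' mean change shifts by the same amount in both arms and the difference is unaffected. Bias needs dropout, or the effect of age, to differ by arm, and the documents show neither. The protocol also plans telephone mobility assessment, with multiple imputation or joint modelling, for informative dropout.

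Finally, the precision argument covers only the linear items. Item 3a is a random-intercept ordinal model, in which adding covariates changes the conditional odds ratio being estimated.

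**Conclusion.** The omission is real and unexplained, and it departs from the protocol's prespecified covariates. The 85% holds for the covariate-adjusted month-36 regression in protocol 8.2 and for nothing in the SAP. The power of the SAP change model cannot be derived from the documents: it runs from about 65% to 99% for correlations of 0.3 to 0.8 and passes 85% at about 0.57. These figures assume two-sided alpha 0.05, 140 complete pairs, equal variance at the two visits and the protocol's minimum detectable effect. The gain from restoring the covariates is likely a few points at most, and its exact size is unknown. The case for the change is consistency with the protocol, a cheap gain in precision and a clear statement of which gait-speed analysis is primary. It is not a case that the planned comparison is invalid or underpowered.

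**What to change.** 1. In SAP items 1a, 2a, 4a and 5a add age, sex and baseline 24-h systolic BP, each with its visit interaction. Keep the covariate-free model as a sensitivity analysis.
2. State that the 85% applies only to the covariate-adjusted month-36 regression of protocol 8.2, and that this regression remains the primary gait-speed analysis unless it is expressly replaced.
3. Deal with ordinal item 3a separately: decide whether a covariate-conditional odds ratio is wanted, and say so.

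The cost is a short SAP amendment and six extra parameters (three main effects and three visit interactions) in about 140 complete pairs. No new data are needed, since all three covariates are available at baseline.

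### SAP items 1a, 2a, 4a and 5a estimate a baseline arm difference that randomisation makes zero in expectation, so they give up precision that a common-baseline model would recover at no cost

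*SAP*

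**What the plan says.** SAP items 1a (white matter hyperintensity), 2a (mobility, cognition, Geriatric Depression Scale), 4a (diffusion imaging) and 5a (sleep and SF-36) share one pair of linear equations. The baseline equation holds an intercept, an arm term beta_C and a random intercept. The month-36 equation adds a time effect beta_L and an arm-by-time term beta_T, which is the parameter of interest. No covariates enter. Of beta_C the SAP says that it "will be zero if the two groups are exactly comparable in their baseline values". Item 3a puts the same linear predictor into an ordinal logistic model. Protocol 8.2, model (c), also has an arm term at T0.

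Protocol section 4 says that "200 will be randomized in a 1:1 ratio to either the intensive or standard treatment arms". Protocol 5.6.2 places the baseline mobility and cognitive tests before randomisation.

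The only power statements are in Protocol 8.3. For gait, "140 participants (70 in each group) will give us 85% power to observe an increase in r^2 of 0.0533 to 0.1800", on top of covariates for which the earlier cohort gave the following: "covariates age, sex, and 24 hour systolic BP at baseline showed an r^2 of 0.1267". For white matter hyperintensity the claim is "85% power to observe an increase in r^2 of 0.0540 for the effect of the treatment arm, to 0.1702". The gait figure refers to analysis (a) in Protocol 8.2: "Multiple linear regression will be performed with treatment group (intensive vs. standard) as the predictor of interest".

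**The concern.** The wording of beta_C treats baseline comparability as something to be found in the data. In a 1:1 randomised trial with baseline tests done before allocation, any baseline difference between the arms as randomised is chance. Estimating it has a price: beta_T subtracts the whole observed baseline difference from the month-36 difference. Because the two measurements are imperfectly correlated, only part of a chance imbalance carries forward, so full subtraction over-corrects and adds noise.

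Precision is at stake. These items are the SAP's only specified treatment comparisons for these outcomes, most are repeated in strata, and the protocol expects only 140 completers from one site.

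**Working it through.** **1. Reproduce the stated power.** Inputs from Protocol 8.3: N = 140, covariate R² = 0.1267, increase 0.0533, full R² = 0.1800. Alpha is not stated; two-sided 0.05 is assumed.

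- f² = 0.0533/(1 − 0.1800) = 0.0650, and the noncentrality is 140 × 0.0650 = 9.10.
- The noncentral F on 1 and 135 df gives 84.97%. The hyperintensity figure gives 85.01%.
- Alpha 0.10 would give 91.3% and alpha 0.025 would give 77.3%, so two-sided 0.05 is the match.

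**2. What beta_T is in the linear items.** With complete pairs, the four fixed effects fit the four arm-by-visit means exactly, so beta_T is the difference in mean change. Mixed-model fits to 150 simulated trials at each of rho 0.4 and 0.7 agreed with the raw change contrast to within 10⁻¹⁴.

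**3. Variance, completers only.** Let n be completers per arm, sigma² the within-arm variance (equal at both visits) and rho the baseline-to-month-36 correlation.

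- Free beta_C: (2·sigma²/n) × 2(1 − rho).
- Common baseline mean: (2·sigma²/n) × (1 − rho²).
- Ratio: (1 + rho)/2, a saving of (1 − rho)/2. This is 25% at rho 0.5 and 15% at rho 0.7.

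If the month-36 SD is k times the baseline SD, the saving is proportional to (1 + k² − 2k·rho) − k²(1 − rho²) = (1 − k·rho)², which is never negative.

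**4. Variance with 100 baselines and 70 completers per arm, dropout at random.**

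- Free: 2·sigma² × [(1 − rho²)/70 + (1 − rho)²/100].
- Constrained: 2·sigma² × (1 − rho²)/70.
- Rho 0.5: 0.01071 + 0.00250 = 0.01321, a saving of 0.00250/0.01321 = 18.9%.
- Rho 0.7: 0.00729 + 0.00090 = 0.00819, a saving of 0.00090/0.00819 = 11.0%.

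**5. Illustration in power units.** Take the planned gait effect, with treatment independent of the covariates. In total-SD units it is 2 × √0.0533 = 0.4617, and the within-arm variance is 1 − 0.0533 = 0.9467. At rho 0.5 with 70 per arm:

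- Free: 0.4617/√(2 × 0.9467/70) = 2.81.
- Constrained: the variance is 0.75 × 0.9467 = 0.7100, so 0.4617/√(2 × 0.7100/70) = 3.24.

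The noncentral t (138 df free, 137 df constrained) gives:

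| rho | free, completers only | free, all 200 baselines | constrained |
|---|---|---|---|
| 0.3 | 65.4% | 70.2% | 83.2% |
| 0.4 | 72.1% | 76.1% | 86.0% |
| 0.5 | 79.6% | 82.6% | 89.6% |
| 0.6 | 87.6% | 89.5% | 93.6% |
| 0.7 | 94.9% | 95.8% | 97.4% |
| 0.8 | 99.3% | 99.4% | 99.6% |

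Power reaches 85% at rho 0.57 (free, completers only), 0.53 (free, all baselines) and 0.37 (constrained). Rho appears in neither document, so the range is an assumption.

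**The case against.** The SAP models are valid. Change from baseline is the outcome that the protocol names, and beta_T estimates it directly and without bias over randomisations. This stands: the point is about precision only.

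A reader might infer that the trial misses its 85% power. The documents do not support that. The 85% was calculated for the month-36 regression, which leaves out baseline gait, and only gait and hyperintensity have such a figure. The SAP introduces its content as added secondary analyses, although sub-item a of items 1 to 4 is labelled primary. At rho 0.6 and above the SAP model itself exceeds 85% for the gait effect.

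A reader might also extend the point to every treatment model in the SAP. Item 7c, a Poisson regression on assignment, has no baseline term. In item 3a beta_T is a difference in log odds ratios, so the constraint applies but the variance and power figures do not.

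Nor does the SAP state equal residual variances. It writes a separate residual for each visit and is silent on whether their variances match. With beta_C free and complete pairs, the choice would not alter the beta_T estimate.

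The last objection limits the remedy. Randomisation equalises expected baselines only among everyone randomised. Item 1h selects patients by achieved blood pressure with arm-specific rules, and the Missing Data text in Protocol 8.2 restricts the primary efficacy analysis to completers while expecting informative attrition. A common baseline mean is not guaranteed in such subsets.

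**Conclusion.** The point holds as an avoidable loss of precision in items 1a, 2a, 4a and 5a, with the same unneeded term in item 3a. Among completers the variance of beta_T can be cut by (1 − rho)/2, which is 25% at rho 0.5 and 15% at rho 0.7. Put as sample size, that equals 1/0.75 = 1.33 or 1/0.85 = 1.18 times as many completers. If all 200 baselines already enter the mixed model, the cut is about 19% and 11%. At the planned gait effect with 140 completers the gain is about 10 power points at rho 0.5 and 2 to 3 at 0.7.

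These sizes assume equal variances at the two visits, two-sided alpha 0.05, no other covariates and, for the 200-baseline case, dropout at random. The direction does not depend on rho; the size does. It is neither bias nor a missed stated power.

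**What to change.** For the randomised comparisons in items 1a, 2a, 4a and 5a:

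- delete beta_C·x_i from both equations, so that the arms share one baseline mean;
- include every randomised patient with a baseline value;
- use an unstructured 2×2 covariance, because once the baseline means are tied the weight given to baseline depends on the covariance model;
- keep beta_T as the estimand.

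Apply the same constraint to item 3a and to the T0 arm term in Protocol 8.2 model (c). In item 1h, where patients are selected after randomisation, keep beta_C or adjust for baseline.

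The cost is one model term and a covariance statement. No new data are needed, and validity under randomisation is kept. The SAP is dated 24 September 2018, ahead of the October 2018 database lock that it cites, so the change fits within pre-specification.
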